7.4.4.6 Conjunctival staining with lysmine green

After the revision with fluorescein, a drop of saline solution will be applied to the tip of the green lysam strip, allowing it to sit on the strip for 5 seconds to elute the dye. A drop of the strip is instilled at the bottom of the temporal sac, while the patient looks upwards, without damaging the conjunctiva. The patient may be asked to blink repeatedly to prevent accumulations in the conjunctival folds. The examination should be done between 1 and 4 minutes after instillation through a neutral density filter or with the red-free filter. It will be graded according to the Oxford scale. [48]

The PI will record in the file and the FRCE the grade granted for fluorescein staining of DO and OS, respectively.

Management as AE: corneal stains that are equal to or greater than grade III will be considered as AEs.

7.4.4.7 Conjunctival hyperemia

Conjunctival hyperemia is defined as the simplest reaction of the conjunctiva to a stimulus, with a red appearance secondary to vasodilation of the conjunctival vessels of variable intensity. It will be graduated using the Efron scale. [49] See annex 16.3 Efron's scale.

Management as AS: conjunctival hyperemias classified as grade 3 or higher will be considered as AD.

7.4.4.8 Chemosis

It is defined as conjunctival edema, the result of an inflammatory reaction. It is qualified as present or absent. The evaluator will use a narrow beam of light at 60° and will measure whether the conjunctiva separates from the sclera by $\geq 1/3$ of the total eyelid opening or if it exceeds the gray line. [50] Management as an EA: its presence will be considered as an EA.

7.5 Study visit and activities program

7.5.1 Description of activities per visit

The procedures are listed in the order in which they are suggested to be performed, trying to maintain the coherence of the evaluations and as far as possible, from the least invasive to the most invasive.

7.5.1.1 Counting Visit

- Signature of the CRF: refers to the signing of the written informed consent document. Without obtaining informed consent, it is not possible to perform any of the study procedures.
- Clinical history: refers to the technical, clinical and legal document in which the patient's health conditions, medical acts and other procedures performed on the patient are chronologically recorded. It includes anthropometric measurements, anamnesis, comprehensive ophthalmological examination that allows discerning the patient's eligibility, that is, evaluation of both eyes of ocular adnexa, slit lamp examination of the ocular surface and anterior segment and fundoscopy. If the patient is taken from the established population base of the study center, the existing medical history may be used, and only one update must be made.
- Evaluation of concomitant medications refers to the questioning by the PI of the patient, inquiring about the use of medications.

- Urine pregnancy test: This refers to performing a rapid pregnancy test on all women of childbearing potential who wish to enter the study. By fertile age we mean women who have had their menarche and have not presented their menopause. Menopause is defined as 12 months from the last menstruation in women over 40 years of age, or who have had a hysterectomy or bilateral oophorectomy. Women of childbearing potential with contraceptive methods including bilateral tubal obstruction should be tested for pregnancy. This test will be performed by the IP or designated team person in accordance with the instructions on the device provided by the sponsor.
- Vital signs: refers to the measurement of heart rate, respiratory rate, systemic blood pressure and temperature. This information must be contained in the patient's medical history and the evolution notes of the patient's clinical file.
- OSDI: see section 7.4.4.2 OSDI score.
- CVAM: see section 7.4.4.3 Better corrected visual acuity.
- Ocular surface stains: see points 7.4.4.5 Corneal and conjunctival staining with fluorescein and 7.4.4.6 Conjunctival staining with lysmine green.
- Comprehensive ophthalmological evaluation: see point 7.4.4.1 Adverse events.
- Eligibility criteria: refers to the review by the PI, where it is found that the patient can be included in the study by meeting the inclusion criteria and not meeting the exclusion criteria.
- Evaluation of AEs: see section 7.4.4.1 Adverse events.

It will be at the discretion of the principal investigator whether the clinical evaluations that will be considered the baseline values of each variable will be those evaluated during the screening visit, or if he or she considers it necessary to repeat any test during the baseline visit. In the latter case, these results should be considered as baseline values.

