3.3 Hypothesis

H_0 = The Humylub Ofteno® PF ophthalmic solution is not inferior in its efficacy compared to its comparators, after 30 days of treatment, presenting a 35% decrease in the final score of the OSDI test compared to its initial value in at least 30% of exposed patients.

$$H_0: P_A - P_B \leq \delta$$

H_1 = The Humylub Ofteno® PF ophthalmic solution is inferior in its efficacy compared to its comparators, after 30 days of treatment, as it does not present a 35% decrease in the final score of the OSDI test compared to its initial value in at least 30% of exposed patients.

$$H_1: P_A - P_B > \delta$$

4. Study design

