4.2 Rationale for the study design

Humylub Ofteno® PF is a product that is currently available for consumption not only in Mexico, but in several Latin American countries such as: Bolivia, Chile, Colombia, Costa Rica, Costa Rica, Colombia, Costa Rica, Colombia Dominican Republic, Ecuador, Guatemala, Haiti, Honduras, Nicaragua, Panama and El Salvador.

Both the efficacy and safety of its compounds, HS and CS, have been proven for use as a treatment for SOS, reducing both the signs and symptoms associated with this pathology. There are several ophthalmic solutions on the market that contain these compounds, including the comparators chosen for this study, Hyabak® and Lagricel® PF. The latter are composed of sodium hyaluronate, at different concentrations, and are also used for the treatment of SOS. One of the main purposes of SOS treatment is to reduce the symptoms described by patients such as burning, SCE, blurred vision, etc. The objective evaluation of these is carried out through internationally approved and accepted questionnaires, which are described in reference documents such as the TFOS DEWS II. One of these tools is the OSDI, the results of which will be considered in this study as the primary outcome variable. Like most efficacy studies for lubricating eye solutions, assessing improvement in patient-reported symptoms compared to reference products is the primary objective of this study. [36]

Due to the differences in the presentation of Humylub Ofteno® PF with one of its comparators, Hyabak®, and thanks to the characteristics of its bottles, this will be an open-label study.

Finally, considering the evaluation of the secondary variable of TRL efficacy by means of a non-invasive method, and since the equipment required to carry out this assessment is not so widely disseminated in ophthalmological offices and clinics in general, multiple research centers will be in charge of executing this study.

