7.4 Outcome variables

7.4.1 Primary outcome variables

- OSDI score (TE: visits 1 and final).

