7.5.1.2 Basal Visit

- Eligibility criteria: refers to the review by the PI, where it is found that the patient can be included in the study by meeting the inclusion criteria and not meeting the exclusion criteria.
- Evaluation of AEs: see section 7.4.4.1 Adverse events.
- TRLNI: see point 7.4.4.4 TRLNI.

- IP randomization: refers to determining the intervention that the patient will follow during the study. This assignment will be made at baseline visit (day 0). See point 7.3 Randomization
- Delivery of the PI and initiation of intervention refers to the delivery of the PI to the study patient, by the research center.
- Delivery of patient material and filling instructions refers to the delivery by the PI to the patient of the patient's diary, ID card and calendar improving adherence. The staff assigned by the research center will carry out prior training to the patient, on the completion of the diary.

7.5.1.3 Visit 1

- Evaluation of concomitant medications: see point 7.5.1.1 Screening Visit.
- Vital signs: refers to the measurement of heart rate, respiratory rate, systemic blood pressure and temperature. This information must be contained in the patient's medical history and the evolution notes of the patient's clinical file.
- OSDI: see section 7.4.4.2 OSDI score.
- CVAM: see section 7.4.4.3 Better corrected visual acuity.
- TRLNI: see point 7.4.4.4 TRLNI.
- Ocular surface stains: see points 7.4.4.5 Corneal and conjunctival staining with fluorescein and 7.4.4.6 Conjunctival staining with lysmine green.
- Comprehensive ophthalmological evaluation: see point 7.4.4.1 Adverse events.
- Evaluation of AEs: see section 7.4.4.1 Adverse events.
- Evaluation of adherence: see point 7.5.1.1 Scrutiny visit.

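### The baseline OSDI is left to investigator discretion, with no criterion for repeating it and no requirement that a repeat precede open-label allocation

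*Combined protocol and SAP*

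**What the plan says.** - **Who sets the baseline.** Section 7.5.1.1 (screening visit): "It will be at the discretion of the principal investigator whether the clinical evaluations that will be considered the baseline values" of each variable are the screening results, or whether a test needs repeating at the baseline visit. If a test is repeated: "In the latter case, these results should be considered as baseline values". No reason for repeating has to be met or recorded, and no variable is excepted.
- **What depends on it.** Section 7.4.1 lists the primary outcome only as "OSDI score (TE: visits 1 and final"), and Section 7.4.4 assigns it ANOVA. The responder definition comes from Section 3.3: "presenting a 35% decrease in the final score of the OSDI test compared to its initial value in at least 30% of exposed patients". Section 10.2.2 builds the sample size on the same 35% fall in 30% of patients, with a 10% margin, though there it refers to the initial mean value.
- **When allocation occurs.** Section 7.5.1.2: "This assignment will be made at baseline visit (day 0"). Section 4.2: "this will be an open-label study".
- **Where a repeat OSDI would fall.** The patient schedule (Section 1.3) has OSDI at screening, visit 1 and the final visit. Neither it nor the activity list in Section 7.5.1.2 places an OSDI at the baseline visit. Section 7.5.1 says of the lists: "The procedures are listed in the order in which they are suggested to be performed".
- **What is absent.** Section 10 has no definition of baseline that would override Section 7.5.1.1. Section 7.3 mentions a computer-based assignment system but does not describe concealment.

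**The concern.** The responder criterion divides by the baseline, so the choice of baseline can change a patient's status. A final OSDI of 15 is a 25% fall from 20, which is not a response, and a 37.5% fall from 24, which is. If the source of the baseline varies between patients for unstated reasons, some patients are judged against their qualifying score and others against a later reading.

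The more serious risk is the timing. Repeat and allocation share one visit, the products are not masked, and OSDI is a self-completed symptom questionnaire. If a repeat is done, or the decision to repeat is taken, once the arm is known or guessed, the baseline is no longer independent of treatment. In a non-inferiority trial with a 10-point margin, a shift of a few points in one arm only would matter. The baseline OSDI also sets the trigger for a lack-of-efficacy adverse event in Section 7.4.4.2 (a rise of at least 40%).

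**Working it through.** The plan gives no figure for the effect of its baseline rule and no retest SD for OSDI. The sizes below are therefore illustrations under stated assumptions.

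**Inputs from the documents.** Response is a fall of at least 35%, that is, final score ≤ 0.65 × baseline (Sections 3.3 and 10.2.2). Planned responder rate 30% and margin 10 points (Section 10.2.2). Entry requires OSDI ≥ 13 (Section 5.1.1). OSDI 23 is where the moderate band begins (Section 7.4.4.2). A repeat replaces the screening value (Section 7.5.1.1).

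**Single-patient arithmetic.** (20 − 15)/20 = 25%; (24 − 15)/24 = 37.5%.

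**Set-up A (assumed).** True OSDI uniform on 13 to 33; screening score = true score + error, kept if ≥ 13; a repeat has independent error of the same SD; individual response SD 0.25; mean response tuned so that 30% respond when screening is the baseline.

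| Retest SD | Screening only | Repeat if screening < 23 | Repeat if screening ≥ 23 | Repeat everyone |
|---|---|---|---|---|
| 2 | 30.0% | 30.2% | 29.2% | 29.5% |
| 4 | 30.0% | 31.1% | 27.4% | 28.5% |
| 6 | 30.0% | 31.9% | 25.6% | 27.5% |

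Repeating low scorers, over screening alone: 30.2 − 30.0 = 0.2; 31.1 − 30.0 = 1.1; 31.9 − 30.0 = 1.9 points.
Opposite habits: 30.2 − 29.2 = 1.0; 31.1 − 27.4 = 3.7; 31.9 − 25.6 = 6.3 points.

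**Set-up B (assumed).** True mean 30, SD 10; mean response 27%, SD 25 points; retest SD 4, 6 and 8; the split is at the median screening score.

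| Retest SD | Repeat low scorers vs screening | Repeat everyone vs screening | Repeat high scorers vs screening | Opposite habits |
|---|---|---|---|---|
| 4 | +1.1 | −0.7 | −0.7 − 1.1 = −1.8 | 1.1 + 1.8 = 2.9 |
| 6 | +1.9 | −1.4 | −1.4 − 1.9 = −3.3 | 1.9 + 3.3 = 5.2 |
| 8 | +2.5 | −2.1 | −2.1 − 2.5 = −4.6 | 2.5 + 4.6 = 7.1 |

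The fourth column follows because low and high scorers are separate groups: the shift from repeating everyone is the sum of the two partial shifts. A rerun of both set-ups with a different random seed agreed to within about 0.1 point in A and a few tenths in B.

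**Reading the tables.** The treatment effect is the same in every column; only the repeat habit changes. If habits are the same in all arms, the shift is common to them. The opposite-habits figure becomes a difference between arms only if one arm is handled one way and its comparator the other, which requires the decision to follow or anticipate allocation. The simulation does not cover a further possibility: answers to a repeat OSDI that are themselves affected by knowing the product.

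**The case against.** The case for leaving the text alone has real substance.

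1. **A reader might infer that the investigator can take the higher of two readings.** In set-up B that rule would raise the responder rate by 6.1, 7.5 and 8.2 points at SDs of 4, 6 and 8. Section 7.5.1.1 does not allow it: a repeat counts whether it is higher or lower, and the choice to repeat is made before its result is seen and a month before the final score. These figures do not describe the plan.
2. **A reader might also infer that discretionary baselines pull the arms together.** With a second arm responding 10 points less in set-up B, the responder difference under screening alone was 12.0, 10.7 and 9.4 points. With low scorers repeated it was 12.2, 10.9 and 9.6. There is no shrinkage.
3. **A repeat may differ little from screening.** The visits are 0 to 2 days apart (Section 1.3) and OSDI recalls the past week, so the true retest SD may lie at the low end of the assumed range. This stands, but it also means little is lost by removing the option for OSDI.
4. **A repeat is not necessarily free of regression to the mean.** Eligibility is reviewed again at the baseline visit, so a repeated score could itself be a qualifying score. This stands.
5. **The listed order puts randomisation after the baseline assessments, and nothing provides for testing after allocation.** True, but the order is only suggested and OSDI is not in that list, so the documents do not exclude it either.
6. **The percentage fall is not the listed primary variable.** Correct: it comes from the hypothesis and the sample-size section. Those are where the margin is applied, and a repeated-measures analysis of OSDI that includes baseline would use the same value.

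**Conclusion.** The point holds in a limited form. The plan lets the baseline of any variable, OSDI included, be changed at the investigator's discretion with no criterion. It does not require that this happen before an open allocation made at the same visit.

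Under assumed retest SDs of 2 to 8 points, selective repeating adds roughly 0 to 2.5 points to the responder rate over screening alone, and opposite repeat habits differ by about 1 to 7 points against the 10-point margin. If every repeat preceded a concealed assignment, the result would be extra noise and a shift shared by all arms. Bias between arms needs a repeat that follows or anticipates allocation, which the documents neither describe nor rule out. That discretion would operate patient by patient is the natural reading, since no site-level or trial-level rule is given, but it is not stated. The sample size is not affected. The change is worth making because it closes a route to bias at almost no cost, not because a large bias has been shown.

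**What to change.** Replace the discretionary paragraph in Section 7.5.1.1 with one rule for all patients, and repeat it in Section 10:

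- The baseline OSDI is the score recorded at the screening visit.
- Any other variable repeated at the baseline visit must be completed and recorded before the allocation is disclosed. Both the screening and the repeat values are kept in the database.

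Fixing OSDI at screening is preferable to a rule based on the last value before randomisation, which would still let the investigator decide who is repeated. Any regression to the mean in a qualifying score is then shared by all randomised arms.

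Cost: a short text change, no added measurement or visit, and no change to the sample size. The one loss is the flexibility to re-baseline OSDI, which is small given the 0-to-2-day gap and the one-week recall.

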7.5.1.2 Basal Visit

- Eligibility criteria: refers to the review by the PI, where it is found that the patient can be included in the study by meeting the inclusion criteria and not meeting the exclusion criteria.
- Evaluation of AEs: see section 7.4.4.1 Adverse events.
- TRLNI: see point 7.4.4.4 TRLNI.

- IP randomization: refers to determining the intervention that the patient will follow during the study. This assignment will be made at baseline visit (day 0). See point 7.3 Randomization
- Delivery of the PI and initiation of intervention refers to the delivery of the PI to the study patient, by the research center.
- Delivery of patient material and filling instructions refers to the delivery by the PI to the patient of the patient's diary, ID card and calendar improving adherence. The staff assigned by the research center will carry out prior training to the patient, on the completion of the diary.

7.5.1.3 Visit 1

- Evaluation of concomitant medications: see point 7.5.1.1 Screening Visit.
- Vital signs: refers to the measurement of heart rate, respiratory rate, systemic blood pressure and temperature. This information must be contained in the patient's medical history and the evolution notes of the patient's clinical file.
- OSDI: see section 7.4.4.2 OSDI score.
- CVAM: see section 7.4.4.3 Better corrected visual acuity.
- TRLNI: see point 7.4.4.4 TRLNI.
- Ocular surface stains: see points 7.4.4.5 Corneal and conjunctival staining with fluorescein and 7.4.4.6 Conjunctival staining with lysmine green.
- Comprehensive ophthalmological evaluation: see point 7.4.4.1 Adverse events.
- Evaluation of AEs: see section 7.4.4.1 Adverse events.
- Evaluation of adherence: see point 7.5.1.1 Scrutiny visit.

7.5.1.4 Final Visit

- Evaluation of concomitant medications: see point 7.5.1.1 Screening Visit.
- Urine pregnancy test: see point 7.5.1.1 Screening Visit.
- Vital signs: see point 7.5.1.1 Scrutiny visit.
- Evaluation of AEs: see section 7.4.4.1 Adverse events.
- OSDI: see section 7.4.4.2 OSDI score.
- CVAM: see section 7.4.4.3 Better corrected visual acuity.

- TRLNI: see point 7.4.4.4 TRLNI.
- Ocular surface stains: see points 7.4.4.5 Corneal and conjunctival staining with fluorescein and 7.4.4.6 Conjunctival staining with lysmine green.
- Comprehensive ophthalmological evaluation: see point 7.4.4.1 Adverse events.
- Evaluation of the Patient's Diary: see point 7.5.1.1 Screening Visit.
- Evaluation of adherence: see point 7.5.1.1 Scrutiny visit.
- Return of PI and patient diary: refers to the return by the patient, the PI and the patient's diary to the research site.

7.5.2 Unscheduled follow-up visits

At the request of the patient or any other individual involved in the study, unscheduled follow-up visits may be conducted for AE reporting. During these visits, all pertinent data on the AEs reported should be collected and, where appropriate, an appropriate management plan should be established.

7.6 Data collection

7.6.1 Source documents

Source documents are all written or printed records derived from automated processes (e.g., printouts of laboratory results issued by automated analysis equipment) where the information is recorded for the first time and that is part of the permanent records of the patient's history. Examples of source documents are the medical history, clinical evolution notes, laboratory reports, cabinet study reports, nursing notes, follow-up notes, surgery records, etc.

The PI is obliged to accept the monitoring of the information related to the study, audits, review by ethics and research committees, and inspections by the health authority, this obligation implies direct access to the source documents.

7.6.2 Electronic forms of data collection

All data related to the protocol will be captured through an eCRF by the research team staff. The data related to the protocol should NOT be captured directly in the eCRF but should be transcribed from the corresponding source document. This procedure allows monitoring to verify the information captured in the eCRF. It is the responsibility of the researcher to ensure that the information is transcribed to the eCRF in a correct, complete, and timely manner. It is understood that all FRCEs captured and submitted for data analysis are approved by the Investigator.

7.6.3 File

The data collected in this database is anonymous (it only stores the patient number together with other information of interest). The program used for data capture and storage covers the traceability requirements necessary for the execution of clinical studies. The data collected will be stored by the sponsor or the clinical research organization designated for this purpose and its storage will have a duration of 10 years. The patient number assignment records will remain in the participating institutions in charge of the PI or his work team and must be kept for at least 5 years.

7.6.4 Unscheduled follow-up visits

At the request of the patient or any other individual involved in the study, unscheduled follow-up visits may be conducted for AE reporting. During these visits, all pertinent data on the AEs reported should be collected and, where appropriate, an appropriate management plan should be established.

8. Evaluation and management of adverse events

8.1 Regulation and regulations on adverse events

The registration and reporting of AEs will be carried out in accordance with the guidelines established in NOM220-SSA1-2016, which is in accordance with the international guidelines ICH E6.

8.2 Definition of Adverse Event

According to the ICH, an AE is any unfavorable medical appearance in a patient under clinical investigation who is administered a pharmaceutical product, regardless of causal attribution.

Therefore, an EA can be any of the following: any undesirable medical event that is temporally related to the use of a medical product, whether or not it is considered related to such a product; any new illness or exacerbation of an existing disease (worsening of the nature, frequency, or severity of a known condition); relapse of an intermittent medical condition (e.g., headache) not present at baseline; any deterioration in a laboratory value or other clinical test (e.g., electrocardiogram [ECG], x-ray) that is related to symptoms or that results in a change in study treatment or concomitant treatment or discontinuation of study medication.

